# 6.3 Method of assigning patients to treatment groups

#### 6.3.1 Recruitment

The study involves one group of patients, distributed in consecutive cohorts, Phase I dose-level 1 and -1, and Phase IIa.

The Investigator will be asked to complete a "screening log" in which each potential patient (i.e. screened patient) will be listed. After having signed the informed consent form, a screened patient is considered as a "consented patient".

Upon satisfaction of all of the inclusion and exclusion criteria for a "consented patient", the patient will be considered as an "eligible patient" for the study. This process is fully documented on the "screening log" should a patient be included or not in the study.

In Phase I, the first enrolled patient will be monitored for safety up to the completion of 3 Pexa-Vec IT injections and 2 nivolumab infusions, scheduled on D29 (i.e. week 4), before the second patient can be enrolled. A security interval of 2 weeks between enrolments of each consecutive patients will be applied. In case of occurrence of a DLT in more than one patient in the first cohort of 6 patients treated at Dose-Level 1, another cohort of 6 patients will be enrolled, who will be treated at the dose de-escalation level (-1).

In Phase IIa, patients will be enrolled without security intervals between consecutive patients.

Under no circumstances will a patient enrolled in the study be permitted to re-enroll for a second time in the study.

#### 6.3.2 Randomization

Not applicable. No randomization is used for this study.

#### 6.3.3 Stratification / Minimizations

Not applicable. Non-viral, viral hepatitis B and C etiologies for HCC will be recorded without stratification on this factor.

### 6.3.4 Dose modifications

No dose modifications for Pexa-Vec or nivolumab are permitted outside protocol-specified conditions for dose de-escalation in Phase I and in Phase IIa detailed in sections 6.1 and 6.2.

#### 6.3.4.1 Management of nivolumab-specific Adverse Events

Toxicities associated or possibly associated with nivolumab treatment should be managed according to standard medical practice. Additional tests, such as autoimmune serology or biopsies, may be used to determine a possible immunogenic etiology.

Although most immune-related adverse events observed with immunomodulatory agents have been mild and self-limiting, such events should be recognized early and treated promptly to avoid potential major complications.

Discontinuation of nivolumab may not have an immediate therapeutic effect and in severe cases, immune-related toxicities may require acute management with topical corticosteroids, systemic corticosteroids, mycophenolate, or TNF- $\alpha$  inhibitors.

The primary approach to Grade 1-2 immune-related adverse events is supportive and symptomatic care with continued treatment with nivolumab; for higher grade immune-related adverse events, nivolumab should be held and oral/parental steroids administered. Recurrent Grade 2 immune-related adverse events may also mandate holding nivolumab or the use of steroids. Consideration for benefit/risk balance should be made by the investigator, with consideration of the totality of information as it pertains to the nature of the toxicity and the degree of clinical benefit a given patient may be experiencing prior to further administration of nivolumab. Nivolumab should be permanently discontinued in patients with lifethreatening irAEs.

## 6.3.4.2 Guidelines for Treatment Interruption or Discontinuation

Nivolumab treatment will be given as long as the patient continues to experience clinical benefit in the opinion of the investigator, and discontinued in case of unacceptable toxicity, symptomatic deterioration attributed to disease progression, or any of the other reasons for treatment discontinuation.

Patients may temporarily suspend study treatment for up to 42 days from the last dose if they experience toxicity that is considered related to the study drug and requires a dose to be held. If nivolumab is held because of adverse events for >42 days beyond the last dose, then the patient will be discontinued from nivolumab.

If a patient must be tapered off steroids used to treat adverse events, nivolumab may be held for additional time beyond 42 days from the last dose until steroids are discontinued or reduced to prednisone dose (or dose equivalent)  $\leq 10 \text{ mg/day}$ . The acceptable length of interruption will depend on an agreement between the investigator and the Coordinating Investigator.

Dose interruptions for reason(s) other than toxicity, such as surgical procedures, may be allowed with Coordinating Investigator approval. The acceptable length of interruption will depend on agreement between the investigator and the Coordinating Investigator.

Although most irAEs observed with immunomodulatory agents have been mild and self-limiting, such events should be recognized early and treated promptly to avoid potential major complications. Discontinuation of nivolumab may not have an immediate therapeutic effect, and there is no available antidote for nivolumab. In severe cases, -immune-related- toxicities may be acutely managed with topical corticosteroids, systemic corticosteroids, mycophenolate, or  $TNF\alpha$  inhibitors.

Patients should be assessed clinically (including review of laboratory values) for toxicity prior to, during, and after each infusion. If unmanageable toxicity due to nivolumab occurs at any time during the study, treatment with nivolumab should be discontinued.

## **Discontinuation Criteria**

Treatment should be permanently discontinued for the following (applicable for Phase I and Phase II parts of the study):

- Any Grade 2 drug-related uveitis or eye pain or blurred vision that does not respond to topical therapy and does not improve to Grade 1 severity within the re-treatment period OR requires systemic treatment
- Any Grade 3 non-skin, drug-related adverse event lasting > 7 days, with the following exceptions for drug-related laboratory abnormalities, uveitis, pneumonitis, bronchospasm, hypersensitivity reactions, and infusion reactions, and endocrinopathies:
  - o Grade 3 drug-related uveitis, pneumonitis, bronchospasm, hypersensitivity reaction, or infusion reaction of any duration requires discontinuation
  - o Grade 3 drug-related endocrinopathies adequately controlled with only physiologic hormone replacement do not require discontinuation
  - o Grade 3 drug-related laboratory abnormalities do not require treatment discontinuation except those noted below
- Grade 3 drug-related thrombocytopenia > 7 days or associated with bleeding requires discontinuation
- Any drug-related liver function test (LFT) abnormality that meets the following criteria require discontinuation:
  - o AST or ALT  $> 8 \times ULN$
  - o Total bilirubin > 5 x ULN
  - Concurrent AST or ALT > 3 x ULN and total bilirubin > 2 x ULN
- Any Grade 4 drug-related adverse event or laboratory abnormality, except for the following events which do not require discontinuation:
  - Isolated Grade 4 amylase or lipase abnormalities that are not associated with symptoms or clinical manifestations of pancreatitis and decrease to < Grade 4 within 1 week of onset.
  - Isolated Grade 4 electrolyte imbalances/abnormalities that are not associated with clinical sequelae and are corrected with supplementation/appropriate management within 72 hours of their onset
  - Grade 4 lymphopenia or leucopenia
  - Grade 4 drug-related endocrinopathy adverse events, such as adrenal insufficiency, ACTH deficiency, hyper- or hypothyroidism, or glucose intolerance, which resolve or are adequately controlled with physiologic hormone replacement (corticosteroids, thyroid hormones) or glucose-controlling agents, respectively, may not require discontinuation after discussion with and approval from the Coordinating Investigator [as allowed by protocol].
  - Any dosing interruption lasting > 6 weeks with the following exceptions:
  - Dosing delays or interruptions to allow for prolonged steroid tapers to manage drug-related adverse events are allowed. Prior to re-initiating treatment in a

subject with a dosing interruption lasting > 6 weeks, the Investigator must be consulted. Tumor assessments should continue as per protocol even if dosing is interrupted or delayed

- Dosing interruptions or delays lasting > 6 weeks that occur for non-drug-related reasons may be allowed if approved by the Investigator. Prior to re-initiating treatment in a subject with a dosing interruption lasting > 6 weeks, the Investigator must be consulted. Tumor assessments should continue as per protocol even if dosing is interrupted
- Any adverse event, laboratory abnormality, or intercurrent illness which, in the judgment of the Investigator, presents a substantial clinical risk to the subject with continued nivolumab dosing

Management of potentially immune related AEs are described in Appendix 3.

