## 10.9 Toxicity Management

All patients should have blood drawn for laboratory abnormalities assessment before any administration of IMP. Blood draws prior to IMP administration should be tested in the local laboratory.

Management of patients with a DLT within a given dose-escalation cohort: Patients who experience a DLT within a given cohort will be monitored by the Investigator until resolution and the Investigator will report the occurrence of a DLT without any delay or within 24 hours of knowledge or occurrence of the event to Transgene and Transgene representative.

If a patient death occurs within 28 days of the last Pexa-Vec or nivolumab administration due to a serious and unexpected Adverse Drug Reaction (ADR) that is determined by the Investigator or Transgene Medical Monitor to be possibly or probably related to Pexa-Vec and/or nivolumab, further administration of Pexa-Vec /nivolumab will be suspended for ongoing patients. Additionally, further patient enrolment into the study will be suspended and ISC, Ethics Committees (ECs) and Regulatory Authorities will be notified as regards further study handling.

• Management of Adverse Events (other than the formation of pustules)

Patient Management: in case of grade 3 or 4 adverse events considered as related to Pexa-Vec and/or nivolumab, the Investigator should contact Transgene Medical Monitor regarding the management of the patient and to determine if the next administration of Pexa-Vec or nivolumab should be postponed until resolution within an acceptable timeframe (*i.e.* within 30 days) otherwise the Pexa-Vec and/or nivolumab treatment will be stopped (*i.e.* no subsequent injection or infusion, respectively).

• Overall Management in the event of Pustule Formation

Pustule Management: specific precautions should be applied to patients treated with Pexa-Vec, in whom the occurrence of pustules is observed, to prevent contamination from spread of the virus in the environment:

- The infusion sites and any skin lesions should be covered loosely with a non-occlusive bandage (e.g., gauze) held in place with first-aid tape for at least 1 week after treatment. If a blister forms, bandaging of the infusion sites or skin lesions should be continued either until healed or the scab falls off.

- Non-occlusive bandage should be changed at least every 3 days or every time the bandage becomes wet.
- Infectious wastes should be disposed of according to the Institution or local procedures.

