receipt of results. If the laboratory abnormality is confirmed and considered at least possibly related to Pexa-Vec and/or nivolumab, the Investigator should contact the Coordinating Investigator (SC) regarding the management of the patient and to determine if the treatment regimen can be reinitiated once the laboratory abnormality has resolved.

If the laboratory abnormality considered at least possibly related to Pexa-Vec and/or nivolumab has not resolved, the next administration should be postponed until resolution within an acceptable timeframe (*i.e.* within 30 days) otherwise the Pexa-Vec and/or nivolumab treatment will be stopped (*i.e.* no subsequent dosing).

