## **APPENDIX 3**

# GUIDANCE TO THE INVESTIGATOR IN CASE OF IMMUNE-RELATED AES

# **Gastrointestinal Toxicity**

Immune-mediated colitis has been associated with the administration of nivolumab. Diarrhea or colitis was reported in 21% of patients in two trials of nivolumab. Immune-mediated colitis occurred in 2.2% of patients in one trial- of these one patient had Grade 2 colitis, and five had Grade 3 colitis. In the other trial, Grade 3 immune-mediated colitis occurred in 0.9% of patients.

Patients should be advised to inform the investigator if any diarrhea occurs, even if it is mild. Range for time to onset of symptoms of colitis has been 1-6 months.

If the event is of significant duration or magnitude or is associated with signs of systemic inflammation or acute phase reactants (e.g. increased CRP or platelet count or bandemia), it is recommended that sigmoidoscopy (or colonoscopy, if appropriate) with colonic biopsy with three to five specimens for standard paraffin block be performed. If possible, one or two biopsy specimens should be snap frozen and stored.

[figure not shown]
Treatment may be restarted following the resolution of colitis. In addition, if the patient is being managed with corticosteroids, treatment should not be restarted until the steroids have been tapered down to a prednisone dose  $\leq 10$  mg/day. Patients who resume treatment should be monitored closely for signs of renewed diarrhea.

Table on next page provides a summary of dose modification guidelines for gastrointestinal toxicities.

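### Sections 6.3.4.2 and 10.9 overlap on related Grade 3-4 toxicity: one requires a permanent stop where the other allows a postponed dose and resumption, and neither says which prevails.

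*Protocol*

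**What the plan says.** **Section 6.3.4.2, Discontinuation Criteria (protocol).** The list opens with "Treatment should be permanently discontinued for the following (applicable for Phase I and Phase II parts of the study" and includes:

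- "Any Grade 4 drug-related adverse event or laboratory abnormality, except for the following events which do not require discontinuation". The exceptions are isolated amylase or lipase findings, corrected electrolyte disturbances, lymphopenia or leucopenia, and controlled endocrinopathies.
- "Any Grade 3 non-skin, drug-related adverse event lasting > 7 days". Controlled endocrinopathies and most laboratory abnormalities are excepted.
- Grade 3 uveitis, pneumonitis, bronchospasm, hypersensitivity or infusion reaction, whatever the duration.
- Grade 3 thrombocytopenia lasting over 7 days or with bleeding.
- Liver-test thresholds: AST or ALT above 8 times ULN, bilirubin above 5 times ULN, or a lower combined threshold.

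**Section 6.3.4.2, interruption guidelines.** Related toxicity may be managed by a hold of up to 42 days from the last dose: "If nivolumab is held because of adverse events for >42 days beyond the last dose, then the patient will be discontinued from nivolumab". Steroid tapers may extend this.

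**Section 10.9.** For clinical events: "in case of grade 3 or 4 adverse events considered as related to Pexa-Vec and/or nivolumab, the Investigator should contact Transgene Medical Monitor". The purpose is to decide whether the "next administration of Pexa-Vec or nivolumab should be postponed until resolution within an acceptable timeframe", given as 30 days; treatment is stopped otherwise. For confirmed, related Grade 3-4 laboratory abnormalities, the Coordinating Investigator is contacted to "determine if the treatment regimen can be reinitiated once the laboratory abnormality has resolved". If the abnormality has not resolved, the same 30-day limit applies.

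**Section 10.4** describes Section 10.9 as the place for managing Grade 3-4 events related to Pexa-Vec.

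**The concern.** Both sections govern what happens after a serious drug-related toxicity. For a set of events that both cover, one ends treatment and the other leaves resumption open. A site can comply with one page of the protocol while breaching another, and two sites can treat the same event differently while each believes it is compliant.

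The first stake is patient safety, because the disagreement is about re-exposure. The second is the data. Exposure summaries and the SAP tables of adverse events leading to treatment discontinuation (Section 8.8.1.4) would partly reflect which section was read. Phase IIa evaluability, which determines who is replaced and who can enter the Per Protocol set used for overall response rate, can also turn on it.

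**Working it through.** The plan gives no figure to reproduce here. The check sets the rules side by side.

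**Step 1. Do the scopes overlap?** Section 6.3.4.2 applies to drug-related events in both phases. Section 10.9 applies to related Grade 3-4 clinical events, and to Grade 3-4 laboratory abnormalities that are clinically significant, confirmed and related. Its text names both products and both kinds of administration. A nivolumab-related Grade 4 event therefore falls under both.

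For the liver thresholds, SAP Appendix 1 puts Grade 3 AST and ALT at above 5 to 20 times ULN, and Grade 3 bilirubin at above 3 to 10 times ULN. The stop thresholds of 8 and 5 lie inside those ranges, so such values are also Grade 3 abnormalities under Section 10.9.

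**Step 2. Do the outcomes differ?** For events outside the exception lists:

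| Related event | Section 6.3.4.2 | Section 10.9 |
|---|---|---|
| Grade 4 clinical event resolving within 30 days | Permanent stop | Consult; may postpone and resume |
| Grade 3 non-skin clinical event lasting 8 to 30 days | Permanent stop | Consult; may postpone and resume |
| Grade 3 pneumonitis (or another event on the any-duration list) resolving within 30 days | Permanent stop | Consult; may postpone and resume |
| Grade 4 laboratory abnormality, confirmed, then resolved | Permanent stop | Consult; may reinitiate |
| AST or ALT above 8 times ULN, confirmed, then resolved | Permanent stop | Consult; may reinitiate |
| Grade 3 event not on the permanent-stop list (such as a skin event), unresolved at 30 days | Hold allowed to 42 days from last dose | Stop |

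The last row runs the other way. Section 10.9 gives no start date for its 30 days. If they run from onset (an assumption), its limit comes first whenever onset is less than 42 − 30 = 12 days after the last dose.

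**Step 3. Is there a tie-break?** Section 10.9 does not cite the Discontinuation Criteria, and the Discontinuation Criteria do not cite Section 10.9. No general precedence statement links them. Section 6.3.4.1 adds a separate rule for nivolumab: hold for higher-grade immune-related events and stop permanently for life-threatening ones.

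**Step 4. Who approves, and for which product?** For interruptions extended beyond 42 days, the interruption guidelines require agreement with the Coordinating Investigator. For interruptions over 6 weeks, which is the same 42 days, the Discontinuation Criteria name only the Investigator. The opening line of the criteria says treatment without saying whether Pexa-Vec is included, although the last item refers to nivolumab dosing.

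**Step 5. Does it reach the efficacy analysis?** Pexa-Vec is given on D1, D15 and D29, and nivolumab on D15 and D29. Phase IIa evaluability (Section 6.6.2) needs 2 Pexa-Vec and 2 nivolumab administrations, plus a post-baseline radiological assessment or other evidence of progression.

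- Event after D15 dosing and before D29: the patient has 2 + 1. Stopped, the patient is not evaluable and should be replaced. Resumed, the patient can reach 2 + 2 and be counted.
- Event after D29 dosing: 2 + 2 is already met, so the dose requirement is unaffected.

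**The case against.** The best defence is that Section 10.9 is a consultation rule. It sends the investigator to the Medical Monitor or the Coordinating Investigator to decide whether to postpone or reinitiate. It nowhere grants re-dosing to a patient who meets a mandatory stop, so it can be read as subordinate to Section 6.3.4.2. Section 10.4 presents it as the Pexa-Vec rule, while Section 6.3.4.2 is written mainly around nivolumab. The ISC also meets within days of related severe or serious events that may require a decision on study conduct.

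Part of this stands. Re-dosing under Section 10.9 is never automatic, central contacts limit divergence between sites, and events on the exception lists raise no permanent-stop conflict. But the subordinate reading is not written down. Section 10.9 names nivolumab, and the only stop it states for these events is failure to resolve in time.

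Four stronger readings are tempting but not supported:

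- **Appendix 3 contradicts the stop list.** It says "Treatment may be restarted following the resolution of colitis" with no grade limit in that sentence, but the dosing algorithm it points to is missing from the available text. An absent grade limit cannot be inferred.
- **There are three different hold clocks.** Six weeks and 42 days are the same length. Converting the 30 days to time since the last dose requires a start date that the protocol does not give.
- **Phase I evaluability is equally exposed.** Mostly it is not. A patient with a dose-limiting toxicity (DLT) counts as evaluable (protocol Section 6.6.2; SAP Sections 2.3 and 6.1), and many such events would be DLTs.
- **About 3 of 30 patients would be affected.** Applying the 11% Grade 3 AST rate cited for nivolumab alone gives 0.11 × 30 = 3.3. That counts all Grade 3 AST elevations. The share above 8 times ULN is not given, and the other event types are not covered.

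**Conclusion.** The contradiction is in the text and holds for a defined set of events: non-excepted related Grade 4 events; non-excepted Grade 3 non-skin events lasting 8 to 30 days; the Grade 3 events listed for a stop at any duration; and the listed liver thresholds. In each case it applies where the event resolves in time for Section 10.9 to permit resumption. A reverse conflict exists for events off the permanent-stop list that outlast 30 days but fall within the 42-day hold; its extent depends on the unstated start date.

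The effect on Phase IIa evaluability is confined to events before the second nivolumab dose. The number of patients cannot be estimated from the documents. The conclusion rests on the wording alone and assumes that Section 10.9 means what it says in naming both products. It implies no view on which rule is clinically right.

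**What to change.** Amend the protocol so that Sections 6.3.4.1, 6.3.4.2, 10.4 and 10.9 agree:

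1. State which section prevails where they overlap, and cross-refer in both directions.
2. State for each rule whether it applies to nivolumab, Pexa-Vec or both.
3. Make the hold limits consistent, each with its start date.
4. Make the approver for interruptions beyond 6 weeks consistent.

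The sponsor and the ISC decide the content of the rule; the need is only that the passages give one answer. The cost is amendment wording, the approvals that Section 13.1 requires for a change bearing on patient safety, and a letter to sites. No patients, visits or procedures are added.

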## 1.4.1.1.2 Nivolumab

Interim data of a study exploring the safety and preliminary efficacy of nivolumab in HCC support the continued exploration of nivolumab in HCC (NCT016585578) (*El-Khoueiry et al. ASCO 2015*).

A total of 47 HCC patients, who progressed on at least one prior line of systemic therapy, including sorafenib, or were intolerant to or refused sorafenib treatment were exposed to escalating doses of nivolumab, from 0.1 to 10 mg/kg q2weeks. In this Phase I clinical trial, one DLT occurred at 10mg/kg (hepatic decompensation), no MTD has been identified and the 3mg/kg dose has been selected for further expansion of the trial. However, in current studies with nivolumab, 240 mg "flat" dose, corresponding to a 3mg/kg dose for a 80 kg individual, is being used as a standard by BMS, as no additional toxicity was observed previously with 10mg/kg, as compared with 3mg/kg. Complexity and time of preparation of nivolumab infusions is then decreased, as well as involved preparation risks.

[figure not shown]
Most frequent nivolumab-related Grade 3 adverse events were hepatic cytolysis (AST increase, 11%, ALT increase, 9%) and lipase increase (6%). Investigator-assessed best overall response rate (ORR) was 19%, including 5% complete response rate. Disease stabilization as best response was seen in 48% of patients. Most interestingly, duration of responses and of stabilizations appeared to be prolonged, i.e. 1.4 to 12.5 months and 1.1 to 17.3 months, respectively. This may have been translated into 62% of patients being still alive one year after initiation of nivolumab treatment. These preliminary data are used for sample size calculation in the present combination study with Pexa-Vec.

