### Laboratory evaluation:

- Blood analysis (to be performed locally):
  - Hematology

- Complete blood count including RBC, hemoglobin, hematocrit, WBC and differential (neutrophils, lymphocytes, monocytes, eosinophils, basophils), and platelets.
- Biochemistry
  - o Liver tests: total bilirubin, ALT, AST, LDH and alkaline phosphatase.
  - o Renal tests: creatinine, calculated creatinine clearance (Cockroft-Gault method) and blood urea nitrogen (BUN).
  - o Electrolytes: sodium, potassium, phosphorus, calcium, magnesium, bicarbonate, and chloride.
  - o Serum protein, serum albumin.
  - o Glucose
- Coagulation parameters:
  - o INR and aPTT (activated partial thromboplastin time).
- Inflammatory parameters: CRP.
- Women of childbearing potential (WOCBP) will undergo a pregnancy test at screening (blood test), then at baseline, on Day 15, Day 29, Pexa-Vec boost, week 6 and every 6 weeks and end of study-safety visit (urine tests). If positive, an ultrasound scan will be performed to confirm pregnancy.
- Other:
  - o HIV serology
  - o Antinuclear and anti TPO antibodies
  - Thyroid blood tests
  - o AFP
- Urinalysis (to be performed locally):
  - Blood, bilirubin, glucose, ketones, nitrite, pH, protein, specific gravity, urobilinogen, and leukocyte esterase; microscopic if leukocyte esterase is abnormal: bacteria, casts, crystals, epithelial cells, mucous, RBC and WBC counts.

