# Transgene / Confidential Amended Version – Márch 20, 2019

Serum chemistry includes BUN, creatinine, creatinine clearance (Cockcroft-Gault formula), sodium, potassium, magnesium, chloride, bicarbonate, calcium, phosphorus, glucose, total bilirubin, ALT, AST, alkaline phosphatase, LDH, total protein, and albumin.

Urinalysis: Blood, bilirubin, glucose, ketones, nitrite, pH, protein, specific gravity, urobilinogen, and leukocyte esterase; microscopic if leukocyte esterase is abnormal: bacteria, casts, crystals, epithelial cells, mucous, RBC and WBC counts

If positive pregnancy test for women of child-bearing potential (WOCBP) an ultrasound will be performed to confirm pregnancy.

Baseline biopsy should be performed if no archival tumor sample is available to establish HCC diagnosis; optional on-trial biopsy scheduled at the discretion of the investigator for translational research purposes can be performed up to Week 8.

Additional Pexa-Vec boosts may be performed in patients based on a case by case discussion between the investigator and Transgene, on the grounds of individual patient benefit. In any case, Pexa-Vec boosts will be performed no sooner than Week 12 and will be combined with a nivolumab infusion.

Beyond 12 months of treatment, the evaluations will be performed every 12 weeks until documented progression or discontinuation of treatment beyond progression. If study treatments are stopped before documented radiological progression, PFS visits will be performed every 6 weeks to continue radiological assessment until documented progression. m The 28-day safety follow-up visit will be organized at least 28 days after the last treatment intake. In case of prior disease progression, this visit will be merged with the end of study visit. In case of treatment discontinuation without disease progression, the 28-day safety follow-up visit will be distinct from the end of study visit that will only occur after disease progression. In this case, patients will undergo in the meantime PFS follow-up visits.

In case the administrations are distributed over 2 consecutive days, patients will undergo another complete physical examination and recording of vital signs prior to Pexa-Vec administration on the second treatment day.

Every 4 weeks starting at W8

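### Lipase and amylase are on no itemised laboratory panel and not in the SAP grading table, so asymptomatic elevations will be under-ascertained, although the protocol names lipase increase as a frequent Grade 3 nivolumab event and has a Grade 4 rule that refers to both enzymes

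*Protocol*

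**What the plan says.** **The expected toxicity.** Protocol section 1.4.1.1.2 summarises the single-agent nivolumab study in HCC: "A total of 47 HCC patients, who progressed on at least one prior line of systemic therapy", or who were intolerant to or refused sorafenib. On safety it says: "Most frequent nivolumab-related Grade 3 adverse events were hepatic cytolysis (AST increase, 11%, ALT increase, 9%) and lipase increase (6"%).

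**The rule that refers to the enzymes.** The Discontinuation Criteria in section 6.3.4.2 apply to both parts of the study. One item is "Any Grade 4 drug-related adverse event or laboratory abnormality, except for the following events which do not require discontinuation". The first listed exception is "Isolated Grade 4 amylase or lipase abnormalities that are not associated with symptoms or clinical manifestations of pancreatitis", on the further condition that the value falls below Grade 4 within one week of onset.

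**The laboratory panels.** Section 8.1 itemises the biochemistry by group. The liver group reads "Liver tests: total bilirubin, ALT, AST, LDH and alkaline phosphatase"; the other groups are renal tests, electrolytes, protein and albumin, and glucose. The Appendix 1 footnote gives the same content: "Serum chemistry includes BUN, creatinine, creatinine clearance (Cockcroft-Gault formula), sodium, potassium, magnesium, chloride, bicarbonate, calcium, phosphorus, glucose, total bilirubin, ALT, AST, alkaline phosphatase, LDH", followed by total protein and albumin. The synopsis has a shorter list introduced as inclusive. The visit lists in sections 8.2 to 8.12 refer back to chemistry without adding analytes. None of these names lipase or amylase.

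**The analysis.** SAP section 8.8.2 plans shift tables of baseline against worst CTCAE grade for hematology and biochemistry, using the parameters listed in SAP section 11. That list has no row for either enzyme.

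**The concern.** The protocol treats these enzymes as relevant in two places and schedules their measurement in none. Of the three laboratory events it names as most frequent at Grade 3, AST and ALT are measured at every safety draw and the third is not measured at all unless someone asks for it.

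Three things are at stake.

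- **The safety profile.** This is the Phase I primary endpoint and a secondary endpoint in Phase IIa. A low lipase count in the report would partly reflect not having looked, and could not be set against the 6% seen with nivolumab alone.
- **The Grade 4 rule.** Both the rule and its exemption need measured values, and the exemption needs a second value within a week. The asymptomatic cases that the exemption describes are the ones least likely to prompt a test.
- **DLT assessment.** Item 1 of the DLT definition in section 6.2 requires a two-grade increase over baseline for Grade 3-4 non-hematologic toxicity. With no baseline lipase or amylase, even a raised value found by chance has no measured reference.

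**Working it through.** The plan states no figure on this point, so there is none to reproduce. The check is a comparison of the texts, followed by an illustration of size.

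**Step 1: where the enzymes appear and where they do not.**

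| Place | Lipase or amylase? |
|---|---|
| Protocol 1.4.1.1.2, nivolumab safety | Yes: lipase, Grade 3, 6% |
| Protocol 6.3.4.2, Discontinuation Criteria | Yes: exemption within the Grade 4 rule |
| Protocol synopsis, safety laboratory tests | No (list is inclusive) |
| Protocol 8.1, laboratory evaluation | No (itemised) |
| Protocol 8.2 to 8.12, visit lists | No |
| Protocol Appendix 1, flow-chart and chemistry footnote | No (itemised) |
| SAP section 11, graded parameters | No |

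The inclusive wording of the synopsis does not close the gap, because section 8.1 and the Appendix 1 footnote list the chemistry analyte by analyte.

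**Step 2: is the 6% consistent with its source?** The section reports 47 patients. 3/47 = 6.4%, 4/47 = 8.5% and 5/47 = 10.6%, which round to the stated 6%, 9% and 11%. These counts are inferred; the protocol gives only percentages.

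**Step 3: illustration of size.** Assume a Grade 3 rate *p* over the whole treatment period and that every patient is tested. The expected number of patients with an event is *n·p*, and the chance of at least one is 1 − (1 − *p*)^*n*. For *n* = 30 and *p* = 0.06, the expected number is 30 × 0.06 = 1.8 and the chance is 1 − 0.94^30 = 84%.

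| Assumed rate | Expected, n = 30 | P(≥1), n = 30 | Expected, n = 47 | P(≥1), n = 47 |
|---|---|---|---|---|
| 3% | 0.9 | 60% | 1.4 | 76% |
| 6% (cited) | 1.8 | 84% | 2.8 | 95% |
| 10% | 3.0 | 96% | 4.7 | 99% |

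Here 30 is the Phase IIa evaluable target, and 47 is the maximum enrolment in section 3.1.2, which assumes that the de-escalation cohort is used.

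The true uncertainty is wider than 3% to 10%. If the count was 3 of 47, the exact 95% interval is 1.3% to 17.5%, and the chance of at least one event in 30 patients runs from 33% to over 99%.

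**Step 4: what the illustration does not cover.** The same formula gives 31% for the six Phase I patients at 6%. That is a whole-treatment figure, not a DLT-window figure. Nivolumab starts on D15 and the DLT period ends on D29, so only about two weeks of exposure fall inside it and the chance there is lower. The documents give no onset times from which to say how much lower. They also give no Grade 4 lipase rate, so how often the discontinuation rule would come into play cannot be calculated.

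**The case against.** The strongest reply is that the gap is narrower than it looks.

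- **The enzyme line is an exemption, not a trigger.** A reader might infer that a lipase-specific stopping rule has been left without data. The text does not say that. Lipase matters only through the general Grade 4 laboratory rule, and the same section says that Grade 3 laboratory abnormalities do not in general require discontinuation. The 6% is a Grade 3 rate, so it says nothing about how often the rule would apply. This stands.
- **Other routes of capture exist.** Section 6.3.4.1 allows additional tests for suspected nivolumab toxicity. Section 10.4 makes any event found on a laboratory test reportable. Section 10.7 has clinically relevant abnormal results repeated and followed. Section 10.9 has clinically significant Grade 3 or 4 values re-tested within up to five days. A reader might infer that the rule cannot work at all, or that the report will show almost no lipase events. Neither follows: once a raised value is found, the repeat values that the one-week condition needs can be obtained, and symptomatic cases will be recorded. What remains is that no scheduled test finds the asymptomatic case in the first place.
- **The 6% may not transfer.** It comes from 47 mostly pretreated patients at 0.1 to 10 mg/kg, whereas this trial is first-line at a flat dose. This stands, and is why the size is given only as an illustration with a range.
- **Not everything is visible.** The content of section 11.3, most of the Appendix 3 algorithms and the eCRF cannot be seen, so a request for lipase somewhere else cannot be ruled out. The safety panels and the SAP grading list are visible, and that is where such a request would be expected.

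**Conclusion.** The point holds in a limited form. The itemised panels and SAP section 11 are out of step with what the protocol says about lipase in section 1.4.1.1.2 and about both enzymes in section 6.3.4.2. As written, asymptomatic elevations will not be systematically detected, incidence will be biased low and not comparable with the cited 6%, and the Grade 4 rule and its exemption will apply only to patients in whom a test happens to be ordered.

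On the assumptions stated (6% over the whole treatment period, all patients tested), about 1.8 Grade 3 events would be there to find among 30 patients. How many would be missed cannot be said, because the documents do not indicate how often lipase would be tested for cause.

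A reader might go further and conclude that Phase I has a 31% chance of overlooking a DLT. The documents do not support that: the figure covers the whole treatment period, and not every Grade 3 laboratory abnormality is a DLT. The point has no bearing on the ORR analysis, the sample size or the stopping boundaries.

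**What to change.** Reconcile the laboratory panels with sections 1.4.1.1.2 and 6.3.4.2:

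1. Add lipase and amylase to the chemistry lists in the synopsis, section 8.1 and the Appendix 1 footnote, on the blood draws already scheduled and including baseline.
2. Add a row for each to SAP section 11, so that both enter the laboratory listings and the shift tables of SAP section 8.8.2.

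No treatment, discontinuation or DLT rule needs to change for this.

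The cost is two more local assays per draw and some repeat tests for raised values under sections 10.7 and 10.9. There may also be additional laboratory events to assess against DLT item 1. Under that item a Grade 3 laboratory value is excluded only if it is not clinically significant and also returns to Grade 2 or less within 72 hours, so an early repeat draw may be needed to classify it. Because such events could count towards the more-than-one-in-six threshold, the sponsor should recognise this consequence when making the change.

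If the panels are left as they are, the study report should say that lipase and amylase were not measured routinely and that their incidence should not be compared with the single-agent figure.
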